# Table 7: Early Post-Operative / Discharge Procedures and Data Requirements(30 days or discharge, whichever is later)

Patient Status	Complete Implant Card		
Physical Assessment	Heart Rate, Blood Pressure, NYHA		

	classification		
Electrocardiogram	Cardiac Rhythm		
Medication Use	Antiplatelet, Antithrombolytic Therapies		
Coagulation Profile	PTT or INR		
Echocardiography	Exam Date/Interval, clinical evidence of PV leak or regurgitation		
Echo Core Lab	Cardiac output, Ejection fraction, Peak and mean valve gradients, assessment of stenosis or regurgitation, LV structure and function, LV mass, jet velocities		
Adverse Events	All adverse events or complications that have occurred since the valve replacement procedure		

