## 9.0 STATISTICAL ANALYSIS

Please refer to Sections 11.1 - 11.3 for study sample size calculations, and a summary of the study analysis plan . Sections 11.4 and 11.5 address the issues of data poolability and missing data. Unless otherwise noted, all statistical tests will be performed at the  $\alpha$  = 0.05 level.

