## 9.5.2 Hemodynamic Performance

Echocardiography data will be obtained preoperatively, early postoperatively and/or discharge, at 6-months and at 1, 2, 4, 6 and 8 year follow-ups. Descriptive statistics for the continuous echo variables and change from baseline (e.g. mean, standard deviation, and range) will be categorized by time interval and valve size. Regurgitation data will be summarized using frequency at each severity level by time interval and valve size. Improvement in regurgitation at one year will be analyzed via the Jonckheere-Terpstra test. Change at one year from baseline for all other hemodynamic outcomes will be analyzed using paired *t*-tests. These analyses will also be reported for the entire study cohort and also stratified by valve model.

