## 9.7 Missing Data

All statistical tests on the effectiveness endpoints will be performed in two ways: (1) using only those subjects with available required for endpoint analysis and (2) by using the method of last observation carried forward (LOCF). Both methods of analyses will then be compared. However, both methods will be used for the comparison of NYHA classification at 8 year post implant to OPC (75%) and for the comparison of hemodynamic performance one year to baseline for the purpose of investigating the effect of loss-to-follow-up.

NYHA classification and hemodynamic performance will be summarized at each of the follow-up interval. In addition, the NYHA classification will only be statistically compared to OPC at 8 years post implant and only the one year post implant hemodynamic performance will be statistically compared to baseline.

To further demonstrate the impact of lost of the follow-up on the effectiveness calculation; a bootstrapped simulation for missing data imputation will be generated as described below:

For each subject who is alive and for whom NYHA assessment is not available at the 8 year post implant follow up visit (Subject A), the last year for which NYHA data is available will be identified (year X).

This document and the information contained herein is considered Proprietary and Confidential and may not be reproduced, used or disclosed without written permission from Edwards Lifesciences LLC.

Separately, a sub group (Group A) of subjects with the same pre-operative and year X NYHA information as Subject A, available data at 8 year post-implant will be identified.

Subsequently, an observed value from the pool of subjects in sub group A will be selected randomly and used to impute the NYHA classification for subject A at 8 years post implant.

The above steps (1-3) will be performed for each subject who is lost to follow up before the 8 year post implant follow-up visit.

Lastly, steps 1 - 4 above will be repeated 999 times to generate 1000 estimated percentages of subjects with NYHA in classes I or II at 8 years post implant. The central 95th percentile for the 1000 estimated percentages will be calculated.

The central 95th percentile generated by the simulation will reflect the variability in the primary effectiveness endpoint estimate caused by lost to follow up.

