### 4.4.6 Calculated Variables

	Tal	ble 8: Calcula	ated Variables
Variable	Unit	Plausible	Calculated by
		Range	
Stroke Volume	mL	30 – 200	Derived as the product of TVI LVOT
(SV)			(cm)and cross-sectional area of the
			LVOT (= $\pi x$ ((LVOT diameter/2)^2) (cm  )
Cardiac Output	L/min	2.0 - 8.0	Derived as the product of SV (cm  ) and
(CO)			HR (min  ): SV x HR/1000
Cardiac Index (CI)	L/min/m 	1.0 - 4.0	Derived as the ratio of CO (L/min) to
			body surface area.
Effective Orifice	cm 	1.0-8.0	Derived using the continuity equation
Area: Mitral			and the values to TVI MV, TVI LVOT and
Valve (EOA MV)			LVOT cross-sectional area (CSA,
			described above):
			EOA MV = (TVI LVOT x CSA LVOT) / TVI
			MV

The variables listed in Table 8 will be measured.

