	Moderate	Qualitative: angiographic grade 2+; Color Doppler jet area- signs of MR greater than Mild present but no criteria for Sever Mr; Doppler vena contracta width (cm) 0.3-69. Quantitative (cath or echo):Regurgitant volume (ml/beat) 30-59;Regurgitant fraction (%) 30-49; Regurgitant orifice area (cm2) 0.20-0.39.	
	Severe	Qualitative: angiographic grade3-4+; Color Doppler jet area- Vena contracta width > 0.7 with large central MR jet (area > 40% of LA area) or with a wall-impinging jetof any size, swirling in LA; Doppler Vena contracta width > 0.7. Quantitative (cath or echo):Regurgitant volume (ml/beat) >/=60;Regurgitant fraction (%) >/=50; Regurgitant orifice area (cm2) >/=0.40.	
Tricuspid Stenosis		A narrowing of the tricuspid valve opening that increases resistance to blood flow from the right atrium to the right ventricle. Severe tricuspid stenosis is defined as a valve area less than 1.0 cm2.	
Tricuspid Regurgitation		Insufficiency of the tricuspid valve causing blood flow from the right ventricle to the right atrium during systole. Severe regurgitation characterized by Vena contracta width greater than 0.7 cm and Systolic flow reversal in hepatic veins.	
Other Valve, specify location:		Other valve (e.g. pulmonic) valve disease or deterioration reported after the AVR procedure.	
Structural Deterioration		Includes dysfunction or deterioration involving the replacement heart valve (exclusive of infection or thrombosis) determined by reoperation, autopsy or clinical investigation. Refers to changes intrinsic to the valve such as wear, fracture, leaflet escape, calcification, leaflet tear, stent creep, suture line disruption of components of prosthetic valve, new chordal rupture, leaflet disruption, or leaflet retraction of repaired valve.	By definition all are valve related .
	Calcification		
	Leaflet tear		
	Stress Fracture		
	Stent creep		
	Suture line disruption		
	vvear damage		
	Loss of structural integrity	Loss of structural integrity of metallic valve component such as wireform, frame, etc.	

		Other Structural		
		Deterioration,		
		specify:		
Valvular	Non Structural		Any abnormality not intrinsic to the valve itself that results in stenosis or regurgitation	
Valvalai	Dysfunction		of the replacement heart valve. Refers to problems (exclusive of thrombosis and	
	Dyoranotion		infection) that do not directly involve valve components yet result in dysfunction as	

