## Model 6900

Three (3) multi-center, non-randomized, prospective clinical studies were conducted with patients implanted with the Carpentier-Edwards PERIMOUNT Pericardial Bioprosthesis Model 6900 Mitral. Three hundred one (301) patients had isolated mitral valve replacement (MVR) and 62 patients had double valve replacement (DVR), where the aortic valve was replaced with a Carpentier-Edwards PERIMOUNT Pericardial Bioprosthesis aortic model. In the first study, patients were implanted between 1984 and 1986; in the second study, patients were implanted between 1989 and 1994; and in the third study, patients were implanted between 1996 and 1997. Patients were evaluated preoperatively, intraoperatively/at discharge, at 1 year, and annually thereafter.

The adverse event rates were based on 363 patients at nine centers. The cumulative follow-up was 1100 patient-years with a mean follow-up of 3.0 years (SD = 2.4 years, range = 0 to 8.2 years).

In these pooled populations, there were a total of 212 (58.4%) males and 151 (41.6%) females with a mean age at implant ( $\pm$  standard deviation) of 66.1 ( $\pm$  10.7) years. The indications for valve replacement were regurgitation (50.7%), stenosis (25.1%), mixed disease (16.0%) and none (8.3%).

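### The one-year test of EOA change is likely to be biased toward improvement, because preoperative EOA is computed from LVOT flow and mitral regurgitation is probably common before surgery

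*Combined protocol and SAP*

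**What the plan says.** Section 9.5.2 lists the echo time points: "Echocardiography data will be obtained preoperatively, early postoperatively and/or discharge, at 6-months and at 1, 2, 4, 6 and 8 year follow-ups". It then specifies the tests: regurgitation has its own one-year test, and "Change at one year from baseline for all other hemodynamic outcomes will be analyzed using paired" t-tests. Section 9.7 confirms that "only the one year post implant hemodynamic performance will be statistically compared to baseline". EOA, EOA index and performance index are among the hemodynamic outcomes listed in Section 3.3.4.

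Appendix 3, Section 4.4.6, gives the core-lab formula: "EOA MV = (TVI LVOT x CSA LVOT) / TVI" MV, that is, LVOT stroke volume over the mitral time-velocity integral. The core-lab form (Appendix 3, Attachment 4) has one EOA field for every time period, including preoperative. No section excludes or corrects EOA when regurgitation is present.

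Table 7 schedules an echo at discharge or 30 days ("Exam Date/Interval, clinical evidence of PV leak or regurgitation"), and it is read by the core lab.

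**The concern.** The formula is valid only if the flow through the LVOT equals the flow through the mitral valve. With a leaking mitral valve, part of the diastolic inflow returns to the atrium and never reaches the LVOT, so computed EOA is too small. After a competent prosthesis is implanted, the error largely goes. It therefore sits in one member of each pair and passes straight into the tested difference.

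The planned test could then report a significant gain in orifice area that comes partly or wholly from the calculation. For a post-approval study of valve performance, that is the wrong message to draw from the only planned test of EOA.

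**Working it through.** The plan gives no sample size, effect size or SD for these paired tests, so there is no stated figure to reproduce. The check derives the bias from the plan's own formula.

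**Inputs**
- RF by grade (Appendix 8, Mitral Regurgitation): moderate 30-49%; severe "Regurgitant fraction (%) >/=50".
- True area A of a non-stenotic regurgitant valve: 4-5 cm². This is the normal area in Appendix 8, applied here as an assumption.
- One-year EOA, E: 2.5 or 1.5 cm².
  - 2.5 is the size-weighted mean in the predecessor cohorts (method not stated). Model 6900 at 1-2 years: (2×1.8 + 35×2.3 + 46×2.6 + 29×2.6 + 5×2.5)/117 = 2.49. Model 6900P at 1 year: (3×2.3 + 21×2.4 + 59×2.6 + 32×2.5 + 15×2.3)/130 = 2.50.
  - 1.5 is the only prosthesis EOA in the documents labelled as continuity-equation (83 valves, early postoperative series, Appendix 9 literature review).
- Lesion mix (Appendices 4 and 9). Model 6900: regurgitation 184/363 = 50.7%, mixed 58, stenosis 91; regurgitation plus mixed 242/363 = 66.7%. Model 6900P: regurgitation 121/209 = 57.9%, mixed 48, stenosis 32; regurgitation plus mixed 169/209 = 80.9%.

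**Formula**
With mitral regurgitation and no aortic regurgitation, mitral inflow = LVOT flow/(1 − RF). Hence:
- computed preoperative EOA = A × (1 − RF)
- true change = E − A
- computed change = E − A(1 − RF)
- bias = A × RF, always toward improvement
- where the true change is negative, the sign reverses when RF > 1 − E/A

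With aortic regurgitation, LVOT flow exceeds mitral inflow and the error runs the other way.

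**Single regurgitant subject (cm²)**

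| E | A | True change | Computed, RF 30% | RF 50% | RF 60% | Reversal above RF |
|---|---|---|---|---|---|---|
| 2.5 | 4 | −1.5 | −0.3 | +0.5 | +0.9 | 37.5% |
| 2.5 | 5 | −2.5 | −1.0 | 0.0 | +0.5 | 50% |
| 1.5 | 4 | −2.5 | −1.3 | −0.5 | −0.1 | 62.5% |
| 1.5 | 5 | −3.5 | −2.0 | −1.0 | −0.5 | 70% |

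**Whole-cohort mean**
Further assumptions: mixed disease 1.5-2.0 cm² with RF 30%; stenosis 1.0-1.5 cm²; other diagnoses left out. Both lesion mixes and both ends of each range give 16 scenarios for each E.

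One example (model 6900 mix; areas 4, 1.5 and 1.0; E = 2.5):
- True: 2.5 − (184×4 + 58×1.5 + 91×1.0)/333 = −0.24.
- Computed at RF 50%: 2.5 − (184×2 + 58×1.05 + 91×1.0)/333 = +0.94.

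Across scenarios:
- E = 2.5: true mean change −0.24 to −1.23. Computed at RF 50%: +0.42 to +0.94, reversed in 16 of 16. At RF 30%, reversed in 10 of 16.
- E = 1.5: true mean change −1.24 to −2.23. Computed at RF 50%: −0.06 to −0.58, reversed in none. At RF 60%, reversed in 6 of 16.
- The bias at RF 50% is 1.18 to 1.65 cm² for either E (for example 0.94 + 0.24 = 1.18; 0.42 + 1.23 = 1.65).

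**Would a false gain be significant?**
Suppose the computed mean change is +0.5 cm² in 50 regurgitant subjects, with an assumed SD of differences of 0.8-1.2. By normal approximation, the chance of two-sided p < 0.05 is 84-99%.

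**Is the error really one-sided within the pair?**
Moderate or worse regurgitation at 1-2 years was seen in 1 + 2 + 4 + 4 + 1 = 12 of 131 model 6900 subjects (9%), against 66.7% with regurgitation or mixed disease as the indication. Some bias remains at one year, but in far fewer subjects.

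**The case against.** Several counter-arguments have weight.

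- **A reader might infer that the EOA result will have the wrong sign.** The documents do not support that. The 2.5 cm² one-year figure has no stated method. The short-term Doppler series in Appendix 9 gives 2.5 cm² from pressure half-time and 1.5 cm² by continuity, so method alone moves EOA by about 1 cm². With 1.5, an RF of 50% produces no reversal.
- **The 4-5 cm² area is a normal value given to diseased valves.** Rheumatic etiology was 37.2% and 30.6%, and calcification 22.6% and 18.2%, in the two predecessor cohorts. A smaller true area lowers the RF needed for reversal (area 3.0: 16.7% with E = 2.5, 50% with E = 1.5). Once the area is below E, however, there is a true gain that is exaggerated, not reversed.
- **Preoperative baseline is an inference.** It is a strong one: preoperative is the first echo, Section 3.3.4 uses the term that way for EQ-5D, and improvement in regurgitation makes sense only against the replaced valve. That valve may itself be a failed prosthesis (Section 3.2), so it should not be called native throughout.
- **This study's lesion mix is not given.** That most subjects are regurgitant is extrapolated from predecessor cohorts and from Section 2.1, which calls regurgitation the leading mitral lesion.
- **A reader might infer that the plan says nothing about valve performance or deterioration.** It does. Echo variables are summarised at each interval by size and model, and structural deterioration, nonstructural dysfunction, reoperation and explant are analysed in Sections 9.4.2 and 9.4.3. A formal 8-year test would be a preference. Nor do the documents give figures showing that gradients move in opposite directions by lesion.

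None of this removes the bias A × RF, which follows from the formula, and nothing elsewhere in the plan corrects it.

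**Conclusion.** The point holds as a bias, not as a predicted wrong sign. If baseline means preoperative, EOA and EOA index at baseline are understated by the regurgitant fraction in subjects with mitral regurgitation. With a lesion mix like the predecessor cohorts, the mean tested change is shifted toward improvement by roughly 1.2-1.65 cm² at RF 50%, under the area assumptions above. Whether the sign reverses depends on true area, RF and one-year EOA, and the documents do not settle these. Concomitant aortic regurgitation would offset part of the shift. The affected outcomes are secondary, with no success criterion attached; the primary safety and NYHA analyses do not depend on them.

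**What to change.** In Sections 9.5.2 and 9.7:

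1. Define the echo baseline separately for each variable.
2. For EOA, EOA index and performance index, use the discharge/30-day core-lab echo as the reference for the one-year paired test.
3. Report preoperative EOA descriptively, split by lesion. Do not test change from it in subjects with more than mild mitral or aortic regurgitation before surgery.
4. Keep subjects who develop regurgitation after implant. Excluding them would remove failing valves and flatter the device. Report their number and gradients, and give EOA with and without them as a sensitivity analysis.
5. Keep the preoperative baseline for LV mass, cardiac output and cardiac index.
6. In the LOCF version, do not carry the discharge reference itself forward, since that yields a change of zero.

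The cost is SAP wording; the echoes are already scheduled. There are three downsides. Subjects without a usable discharge echo leave the EOA test. Flow conditions soon after surgery differ from those at later visits. Aortic regurgitation is graded only where the exam allows (Appendix 3, Section 4.4.10), so some subjects cannot be classified. Mild mitral regurgitation (RF below 30% in Appendix 8) also leaves a smaller residual bias.

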## 9.6 Poolability

Subject baseline risk will be statistically compared between centers and regions (ie,. United States vs. Canada, United States vs. Europe, United States vs. Asia Pacific, and United States vs. Israel). Chi-square tests will be used to compare categorical risk factors while analysis of variance will be used to compare

This document and the information contained herein is considered Proprietary and Confidential and may not be reproduced, used or disclosed without written permission from Edwards Lifesciences LLC.

continuous risk factors. Comparisons will be based on the following demographic and pre-operative variables: age, sex, etiology, previous heart valve replacement surgery, valvular lesion, pre-operative NYHA, concomitant cardiac procedures, and coexisting cardiovascular conditions. Also included in the analysis will be the size of implant adjusted for both model 7000/7000TFX, model 7200TFX and models 7300/7300TFX according to the TAD. Furthermore, time to event for the following events will be compared between centers via a log-rank statistic: thromboembolism, all hemorrhage, death or explant, and death. Additional analyses may be performed if the need arises.

## 9.7 Missing Data

All statistical tests on the effectiveness endpoints will be performed in two ways: (1) using only those subjects with available required for endpoint analysis and (2) by using the method of last observation carried forward (LOCF). Both methods of analyses will then be compared. However, both methods will be used for the comparison of NYHA classification at 8 year post implant to OPC (75%) and for the comparison of hemodynamic performance one year to baseline for the purpose of investigating the effect of loss-to-follow-up.

NYHA classification and hemodynamic performance will be summarized at each of the follow-up interval. In addition, the NYHA classification will only be statistically compared to OPC at 8 years post implant and only the one year post implant hemodynamic performance will be statistically compared to baseline.

To further demonstrate the impact of lost of the follow-up on the effectiveness calculation; a bootstrapped simulation for missing data imputation will be generated as described below:

For each subject who is alive and for whom NYHA assessment is not available at the 8 year post implant follow up visit (Subject A), the last year for which NYHA data is available will be identified (year X).

This document and the information contained herein is considered Proprietary and Confidential and may not be reproduced, used or disclosed without written permission from Edwards Lifesciences LLC.

Separately, a sub group (Group A) of subjects with the same pre-operative and year X NYHA information as Subject A, available data at 8 year post-implant will be identified.

Subsequently, an observed value from the pool of subjects in sub group A will be selected randomly and used to impute the NYHA classification for subject A at 8 years post implant.

The above steps (1-3) will be performed for each subject who is lost to follow up before the 8 year post implant follow-up visit.

Lastly, steps 1 - 4 above will be repeated 999 times to generate 1000 estimated percentages of subjects with NYHA in classes I or II at 8 years post implant. The central 95th percentile for the 1000 estimated percentages will be calculated.

The central 95th percentile generated by the simulation will reflect the variability in the primary effectiveness endpoint estimate caused by lost to follow up.

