	plasma free hemoglobin (or haptoglobin and SLDH)
	platelet count
	reticulocyte counts

	Primary Effectiveness:			
	Percentage of subjects in NYHA Functional Class I or II at 8 years post implant.			
	Secondary Effectiveness:			
	Hemodynamic Performance at 8 years post implant:			
	Peak gradient			
	Mean gradient			
	Effective orifice area (EOA)			
	EOA index			
	Performance index			
	Cardiac output			
	Cardiac index			
	Severity of mitral regurgitation			
	Left ventricular mass regression			
	Quality of Life Survey (EQ-5D)			
	Edwards Lifesciences LLC			
	[name]			
Study Sponsor:	[name]			
	[contact]			
	[contact]			

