#### 3.3.4 Secondary Effectiveness Endpoints

The secondary Effectiveness endpoints will be:

Hemodynamic Performance by echocardiography at 8 years post implant, which includes:

- Peak Gradient
- Mean Gradient
- Effective Orifice Area
- Effective Orifice Area Index
- Performance Index
- Cardiac Output
- Cardiac Index

This document and the information contained herein is considered Proprietary and Confidential and may not be reproduced, used or disclosed without written permission from Edwards Lifesciences LLC.

- Severity of Valvular Regurgitation
- LV Mass Regression

Quality of Life Survey (EQ-5D) at 6 month post index procedure as compared to preoperative baseline.

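### The secondary hemodynamic endpoint is set at 8 years, but hemodynamics are tested only at one year; the 8-year results are descriptive, with no confidence interval and no analysis of late change

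*Combined protocol and SAP*

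**What the plan says.** Section 3.3.4 defines the secondary effectiveness endpoint as "Hemodynamic Performance by echocardiography at 8 years post implant" and lists gradients, EOA and its index, performance index, cardiac output and index, severity of regurgitation and LV mass regression. The synopsis (section 1.0) gives the same time point: "Hemodynamic Performance at 8 years post implant".

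Section 9.5.2 plans two kinds of test, both at one year. For regurgitation: "Improvement in regurgitation at one year will be analyzed via the Jonckheere-Terpstra test". For the rest, by t-test: "Change at one year from baseline for all other hemodynamic outcomes will be analyzed using paired". Section 9.7 repeats the limit: "only the one year post implant hemodynamic performance will be statistically compared to baseline". The same sentence places the NYHA comparison at 8 years.

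Other visits are described. Section 9.5.2 says "Descriptive statistics for the continuous echo variables and change from baseline (e.g. mean, standard deviation, and range) will be categorized by time interval". The tables are also split by size of valve, with regurgitation tabulated by severity level. Section 9.7 adds "NYHA classification and hemodynamic performance will be summarized at each of the follow-up interval". Echo is required at 6 months and at 1, 2, 4, 6 and 8 years (section 6.1.2 and Table 10).

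**The concern.** The stated purpose (section 3.1) is long-term safety and effectiveness. A comparison at one year shows the early result of the operation. It cannot show how the prosthesis performs at the time point that the protocol chose for this endpoint.

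The sponsor's predecessor data suggest that one year is too early to see durability problems. For model 6900, freedom from structural valve deterioration was 100% at 1 year, 97.6% at 5 years and 92.8% at 8 years (95% interval 85.3 to 100, with 18 patients at 8 years; Appendix 4, Table 1). The reporting guideline reproduced as Appendix 1 says that this hazard rises with time since insertion, and it prefers longitudinal analysis of serial assessments to analysis of the last one alone.

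The planned 8-year change from baseline only partly fills the gap. If baseline means the preoperative state, as section 3.3.4 uses the word for EQ-5D, the change combines the benefit of surgery with any later decline of the prosthesis. A valve could lose ground between year 1 and year 8 and still look better than the diseased valve that it replaced. Comparing the summary means at the two visits does not settle this, because subjects who die or are explanted contribute to the first visit and not to the second.

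**Working it through.** **Endpoint against analysis**

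| Outcome | Endpoint time | Time tested | Plan at 8 years |
|---|---|---|---|
| NYHA class I or II | 8 years | 8 years, exact binomial against 75% | Test, plus missing-data analyses |
| Gradients, EOA and other continuous echo outcomes | 8 years | One year, paired t-test against baseline | Mean, SD, range, change from baseline |
| Regurgitation severity | 8 years | One year, Jonckheere-Terpstra | Frequencies by grade |

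The primary effectiveness endpoint is tested at its own time point; the hemodynamic endpoint is not. The missing-data provisions in section 9.7 follow the same pattern. For hemodynamics, the comparison of available data with last observation carried forward is specified at one year, and the bootstrap imputation covers NYHA only.

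**The plan's own figures**

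No sample size, hypothesis or power is stated for hemodynamics. The figures that fix the 8-year sample are in section 9.1, and they reproduce:
- With 8-year survival of 56% and n = 212, P(X ≥ 102) = 0.9912, above the printed 98.7%.
- Inflation for 15% loss: 212 / (1 − 0.15) = 249.4, rounded up to 250.

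**What the 8-year sample could support**

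Take n pairs of echoes per subject (one early postoperative, one at 8 years), two-sided α = 0.05, and changes measured in units of their own SD.

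- 95% interval half-width = t(0.975, n − 1) / √n. For n = 101: 1.984 / 10.05 = 0.197 SD.
- The detectable mean change comes from the noncentral t distribution.

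| Pairs | 95% half-width (SD) | Detectable at 80% power (SD) |
|---|---|---|
| 101 | 0.197 | 0.281 |
| 80 | 0.223 | 0.317 |
| 60 | 0.258 | 0.368 |

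At 90% power with 101 pairs, the detectable change is 0.326 SD.

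The documents give no SD of within-subject change. If it were 1.4 to 3.0 mm Hg for mean gradient (an assumption), then with 101 pairs:
- half-width: 0.197 × 1.4 = 0.28 to 0.197 × 3.0 = 0.59 mm Hg;
- detectable at 80% power: 0.281 × 1.4 = 0.39 to 0.281 × 3.0 = 0.84 mm Hg.

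The 101 in section 4.0 counts subjects completing 8 years, not subjects with two readable echoes inside the ±1 month windows, so the rows for 80 and 60 pairs are shown.

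**The case against.** The strongest reply is that description is a deliberate choice. Section 3.3.4 states no hypothesis for hemodynamics, section 9.7 plainly limits formal testing, and a single-arm post-approval study may describe a secondary endpoint without testing it. That is fair, and a formal test is not essential. But a described endpoint still needs a stated measure of precision. Nor does the plan say that the 8-year endpoint is meant to be descriptive; it simply tests another time point.

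A second reply is that late failure is already covered, and this is largely right. A reader might infer that late deterioration goes unanalysed. The documents do not support that: structural deterioration and non-structural dysfunction have late linearized rates (9.4.3), time to reoperation and explant is analysed (9.4.2), and Kaplan-Meier freedom from each adverse event is planned (9.3.1). These analyses also keep subjects whose valves failed, which an 8-year echo comparison cannot do. What they leave out is gradual change below the threshold of an event.

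A third reply is that paired 8-year echoes exist only for survivors with the valve in place. This stands. The added estimate describes that group and does not remove the selection.

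A reader might also take the model 6900 gradients in Appendix 4 as proof of late drift: 27 mm, 4.1 (n = 40) at 1 to 2 years against 8.8 (n = 6) at 5 years; 29 mm, 3.5 (n = 47) against 5.1 (n = 5). They are not proof. The groups are tiny and unpaired. In the 27 mm group one value of 25 drives the mean: without it, (6 × 8.8 − 25) / 5 = 5.6. A value of 25 already appears in that group at 3 to 6 months, and in the 29 mm group EOA moves the other way, from 2.6 to 2.9 cm². This point does not rest on those figures.

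**Conclusion.** The mismatch holds: the endpoint is at 8 years, all hemodynamic tests are at one year, and no interval or longitudinal analysis is stated for 8-year hemodynamics or for late hemodynamic change. The plan should be amended, but this is a gap in a secondary endpoint and does not touch the primary analyses.

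It would go too far to say that the 8-year hemodynamic data have no planned analysis, or only cross-sectional ones. Change from baseline is a within-subject summary and is planned at each interval.

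The planned sample size does not explain the omission: on 101 pairs a mean change would be estimated to within about ±0.20 SD, widening to ±0.26 SD on 60. These figures assume approximately normal mean changes and echoes readable at both visits. Any translation into mm Hg depends on the assumed SD of change.

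**What to change.** Amend sections 9.5.2 and 9.7 for the echo outcomes:

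- Report each 8-year estimate with a 95% confidence interval.
- Report the within-subject change from the one-year (or 6-month) echo to the 8-year echo with a 95% confidence interval, choosing one reference visit in advance. Use a paired ordinal method for regurgitation.
- Keep the preoperative reference for LV mass regression, where regression from the preoperative state is the quantity of interest. Leave EQ-5D out, since it is collected only preoperatively and at 6 months.
- Label these results secondary and estimation-focused, which limits the multiplicity problem of testing many echo outcomes. State that they apply to survivors with the valve in place and both echoes, give the number of pairs, and read them beside the structural deterioration and explant analyses.
- Keep the one-year comparison as supportive.

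The cost is SAP wording and one more table, because every echo is already required. The downside is that the estimate describes survivors only. When the timeline in section 4.2 was written (November 2013), the longest follow-up was five years, so the analysis could then have been fixed before any 8-year data existed.
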